11 STATISTICAL CONSIDERATIONS

11.1 STUDY DESIGN

Study CTO # 103048 is a potentially multicenter, non-randomized, single cohort phase IB trial evaluating the safety and efficacy of tarloxotinib in combination with sotorasib in NSCLC patients with KRAS G12C mutation who have progressed on any small molecule KRAS G12C inhibitor.

Safety lead-in

A minimum of 6 patients and as many as 18 patients will be enrolled in a safety lead-in cohort to evaluate the safety of the combination of tarloxotinib and sotorasib. Sotorasib will be held at a fixed dose of 960 mg QD (the approved dose) while the starting dose of tarloxotinib will be the monotherapy RP2D equal to 150mg/m² QW (dose level 1 [DL1]). Following a 3+3 algorithm, an initial 3 patients will be enrolled at DL1. If 0 or 1 of 3 patients experience a DLT, an additional 3 patients will be enrolled to DL1. DL1 will be declared the combination RP2D (RP2D_c) if at most 1 of 6 patients treated at DL1 experience a DLT. Alternatively, if there are 2 or more DLTs observed at DL1, 3 patients will be enrolled at DL -1 and the 3+3 rules repeated for safety evaluation. The RP2D_c will be the highest DL at which at most 1 patient of 6 experiences a DLT. If DL -2 is considered too toxic, additional dose levels below DL -2 to be determined may be considered for safety.

Dose expansion

Once the tarloxotinib RP2D_c is reached, an expansion cohort of up to 12 patients will be enrolled to evaluate the safety of the combination of tarloxotinib and sotorasib. Eligible safety lead-in patients treated at the RP2D_c will be included in the expansion cohort.

The combination of tarloxotinib and sotorasib will not be considered promising if there is weak evidence the true objective response rate (ORR) exceeds 20%. Specifically, the trial will be declared negative if $\text{Prob}(\text{true ORR} > 20\% | \text{observed no. of responses}) < 20\%$, equivalent to observing at most 1 response in 12 patients. We assume the true ORR follows a beta (0.5, 0.5) prior distribution and, conditional on the true ORR, the number of responses follows a binomial distribution. If at least 2 responses in 12 patients are observed, the combination may be considered promising. Given 1 response in 12 patients, the probability the true ORR exceeds 20% is approximately 16%. Given 2 responses in 12 patients, the probability the true ORR exceeds 20% is approximately 42%.

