11.1.2 POPULATIONS FOR ANALYSES

The following analysis sets will be defined for this study.

The **safety analysis set** comprises all enrolled patients who receive any quantity of study treatment, regardless of eligibility. The safety evaluation will be performed based on the first dose of study treatment a patient receives, regardless of the patient's cohort assignment. The safety analysis set will be used for all dosing/exposure and safety analyses.

The **DLT-evaluable population (safety lead-in only)** comprises patients who have either completed the DLT-observation period (1 cycle, 28 days) and received at least 75% of planned doses of the tarloxotinib and sotorasib combination in cycle 1 or have discontinued study treatment or study participation before completing cycle 1 due to a DLT.

The **intention to treat (ITT) analysis set** comprises all patients in the safety analysis set eligible for study inclusion and who meet the inclusion criteria for dose expansion, including eligible safety lead-in patients treated at the RP2D_c. This analysis set will be used for all efficacy analyses.

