11.3 INTERIM ANALYSES

Safety lead-in

Safety and tolerability data will be reviewed on a cohort-by-cohort basis during safety lead-in to determine if an additional cohort of patients should be enrolled at the current DL, if de-escalation is warranted, or if the protocol should be amended to evaluate additional intermediate or lower DLs. The final determination of the RP2D_c will be based on the totality of data including, but not limited to, safety and early signs of anti-tumor activity.

Dose expansion

Interim futility analysis. Given the limited sample size, there will be no futility interim analysis in the dose expansion cohort.

Continuous safety monitoring. Bayesian toxicity monitoring will be used to perform continuous safety monitoring of patients enrolled in the expansion cohort. Specifically, patients enrolled in the expansion cohort will be monitored for incidence of DLT-equivalent (DLT-E) events, defined as any safety event that would have qualified as a DLT had that patient been enrolled in the safety lead-in portion of the study. We assume the true DLT-E rate follows a beta (0.5, 0.5) prior distribution and, conditional on the true DLT-E rate, the number of patients who experience a DLT-E follows a binomial distribution. If $\text{Prob}(\text{DLT-E rate} > 33\% | \text{observed no. DLT-Es}) > 50\%$, trial enrollment will be paused. (Note: The observed number of DLT-Es will include DLTs from eligible safety lead-in patients treated at the RP2D_c who are included in the expansion cohort. Bayesian toxicity monitoring parameters were selected to calibrate with the 3+3 de-escalation rules used in the safety lead-in.) If the trial is paused, the safety review committee will review the totality of the safety data and determine whether to continue patient enrollment at the current RP2D_c, introduce intermediate or lower dose levels for evaluation, or close the trial to accrual and declare the combination of tarloxitinib and sotorasib too toxic. This monitoring rule has a 13% and 95% probability of pausing if the true DLT-E rate is 10% or 50%, respectively. The table below specifies safety monitoring thresholds.

Bayesian toxicity monitoring boundaries		
No. of patients	No. of DLT-Es to pause study	Observed DLT-E rate
6	≥2	≥0.33
7-9	≥3	≥0.33
10-11	≥4	≥0.36
12 – expansion cohort fully accrued		

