12 CORRELATIVE STUDIES

Archived tumor samples or samples from newly obtained tumor tissue will be collected prior to baseline and will be used to confirm mutation status retrospectively in all patients and to assess expression of specific mutations and biomarkers in consenting patients.

Blood samples will be collected for biomarker analysis at Cycle 1 Day 1, Cycle 2 Day 1, and end of treatment. Whole blood samples will be collected in two 10 mL cell-free DNA BCT (Streck) blood collection tubes and two 10 mL BD Vacutainer EDTA tubes with total volume of collection no more than 40 mL. Tumor tissue will be collected for retrospective concordance mutation testing and correlation with biomarkers.

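### The efficacy set labelled ITT drops treated patients judged ineligible, and DLT-E monitoring drops ineligible lead-in patients treated at the RP2D_c

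*Combined protocol and SAP*

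**What the plan says.** Section 11.1.2 (and the Synopsis, Statistical Methods) defines two sets that matter here.

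- The safety set "comprises all enrolled patients who receive any quantity of study treatment, regardless of eligibility". Its use is stated without exception: "The safety analysis set will be used for all dosing/exposure and safety analyses".
- The set labelled intention to treat "comprises all patients in the safety analysis set eligible for study inclusion and who meet the inclusion criteria for dose expansion". Of this set the plan says: "This analysis set will be used for all efficacy analyses". Section 11.2.2 accordingly summarises ORR in it.

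Section 4 holds the only entry criteria in the protocol; there is no separate list for the expansion.

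Section 11.1 gives the efficacy rule in two forms: "the trial will be declared negative if" the posterior probability of a true ORR above 20% is below 20%, said to be "equivalent to observing at most 1 response in 12 patients". Two or more responses in 12 may be considered promising. No count is given for any other number of patients, and no rule is given for replacing patients found ineligible.

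Section 12 says that archived or new tumour samples "will be used to confirm mutation status retrospectively in all patients".

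Section 11.3 monitors everyone enrolled in the expansion cohort for DLT-equivalent events (DLT-Es), with no eligibility condition. For patients carried over from the lead-in it adds: "The observed number of DLT-Es will include DLTs from eligible safety lead-in patients treated at the RP2D_c who are included in the expansion cohort". Section 11.1 likewise admits only eligible lead-in patients at that dose to the expansion cohort.

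**The concern.** A set from which treated patients can be removed on eligibility grounds is not an intention-to-treat set. This is an open-label, single-arm trial, and the plan does not say when eligibility is settled for analysis, by whom, or without knowledge of response. A patient can therefore be judged ineligible after the response is known, and leaving out non-responders raises the ORR. With about 12 patients, one or two such decisions can matter to the primary efficacy rule.

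Retrospective mutation testing is one possible route, since a KRAS G12C mutation is the first inclusion criterion in 4.1. Section 6.5.7 also foresees violations of the entry criteria.

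On safety, whether a patient met the entry criteria does not decide whether the dose caused a toxicity. Filtering the carried-over lead-in patients by eligibility conflicts with the way 11.1.2 defines and uses the safety set, and it changes both the numerator and the denominator of the pausing rule.

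**Working it through.** **Inputs.** From 11.1: beta(0.5, 0.5) prior for ORR, binomial likelihood, negative if Prob(ORR > 20%) < 20%. From 11.3: the same prior for the DLT-E rate, pause if Prob(rate > 33%) > 50%. Assumed, because the documents give no figure: the number of treated patients later judged ineligible, shown here as 0, 1 or 2.

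**Efficacy.** With x responses in n patients, Prob(ORR > 20%) = 1 − F(0.20; 0.5 + x, 0.5 + n − x), where F is the beta distribution function.

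The plan's own figures are reproduced: 1/12 gives 15.5% (stated as about 16%) and 2/12 gives 41.5% (stated as about 42%). The cut of at most 1 in 12 follows.

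Now remove non-responders when there is exactly one response:

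| Non-responders removed | x/n | Posterior | Posterior rule |
|---|---|---|---|
| 0 | 1/12 | 15.5% | negative |
| 1 | 1/11 | 18.8% | negative |
| 2 | 1/10 | 22.6% | not negative |

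With no responses nothing changes: 0/12 gives 1.9% and 0/10 gives 3.2%.

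Exactly one response in 12 is not a rare result. At a true ORR of 10% its probability is 12 × 0.1 × 0.9^11 = 0.377; at 20% it is 12 × 0.2 × 0.8^11 = 0.206.

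The missing rule for other n matters even without selective exclusion. At n = 10 the posterior form needs only one response to avoid a negative result. At a true ORR of 10% that has probability 1 − 0.9^10 = 65.1%, against 34.1% for at least 2 of 12.

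**Toxicity monitoring.** Prob(rate > 33%) = 1 − F(0.33; 0.5 + x, 0.5 + n − x). This reproduces the table in 11.3 (2 at n = 6, 3 at n = 7–9, 4 at n = 10–11). Exact sequential pausing probabilities over looks at n = 6 to 11 are 12.6% and 95.0% at true rates of 10% and 50% (stated as 13% and 95%).

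- Omit one ineligible lead-in patient who had a DLT: 3/9 (52.5%, pause) becomes 2/8 (33.0%, no pause).
- Omit one who had no DLT: 3/10 (43.6%, no pause) becomes 3/9 (52.5%, pause).

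For a six-patient lead-in with one DLT, the table in 11.3 gives the further DLT-Es needed for a pause, with the DLT patient kept or omitted:

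| New patients | Kept | Omitted |
|---|---|---|
| 1 | 3 − 1 = 2 (n = 7) | 2 (n = 6) |
| 2 | 3 − 1 = 2 (n = 8) | 3 (n = 7) |
| 3 | 3 − 1 = 2 (n = 9) | 3 (n = 8) |
| 4 | 4 − 1 = 3 (n = 10) | 3 (n = 9) |
| 5 | 4 − 1 = 3 (n = 11) | 4 (n = 10) |

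The omission raises the requirement after 2, 3 or 5 new patients and leaves it unchanged after 1 or 4.

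**The case against.** **Ineligible treated patients should be few.** Section 5 requires an audit of eligibility source documents before registration. This stands as a limit on the number, not as a bar: 11.1.2 itself provides for treated patients who are ineligible.

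**Section 12 describes concordance testing, not an eligibility decision.** A reader might infer that a discordant result takes the patient out of the efficacy set. No section says so. It is a possible route only.

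**The change in the efficacy rule is a narrow case.** It needs exactly one response, two excluded patients who are both non-responders, no replacement, and the posterior form of the rule. Since 11.1 admits only eligible lead-in patients to the expansion, one found ineligible in time need not take one of the 12 places. All of this stands. A reader might also infer that two exclusions turn a negative trial into a promising one. They do not: one response never meets the stated requirement of at least 2 in 12, so the result lands where the plan has no rule.

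**The toxicity filter is limited, and the DLT is not lost.** A reader might infer that monitoring leaves out every ineligible patient. It does not: patients enrolled directly into the expansion are monitored without an eligibility condition. A DLT in an ineligible lead-in patient still counts in the 3+3 decision, because the DLT-evaluable population has no eligibility condition, and it is reported under 11.2.4. The safety review committee would see it too, but only once a pause has occurred, so that review cannot supply the missing trigger.

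**The filter does not always weaken monitoring.** A reader might infer that an omitted DLT always means one more event before a pause. The patient also leaves the denominator, so this fails after 1 or 4 new patients, and omitting a patient without a DLT tightens the rule.

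**Conclusion.** The point holds in limited form. The set labelled intention to treat is an eligible-and-treated set, and it governs every efficacy analysis. Treated patients can leave the ORR denominator on eligibility grounds, with nothing in the plan to ensure that this is decided without knowledge of response. One excluded non-responder does not alter the posterior rule at one response (18.8%). Two move it from negative (15.5%) to not negative (22.6%), an outcome the plan does not define. How many patients would be affected is an assumption, and the audit before registration makes two less likely.

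Separately, the eligibility filter on carried-over lead-in patients in DLT-E monitoring conflicts with the definition and stated use of the safety set. It can prevent or trigger a pause, depending on whether the omitted patient had a DLT.

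The documents do not show that any exclusion will occur, or that the trial's conclusion would be wrong. The case for change is that a possible bias and an internal conflict can be removed at little cost.

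**What to change.** 1. In 11.1.2 and the Synopsis, define the primary efficacy set as all patients whose first dose of study treatment was at the RP2D_c, regardless of later eligibility findings. Tying it to the first dose follows the safety set's convention and keeps out lead-in patients who started at a higher level and were later reduced. Drop the condition about expansion-specific criteria, or define it.
2. Keep the eligible-only set as a sensitivity analysis, and do not call either set intention to treat.
3. In 11.1, apply the posterior negative rule to the actual n and state the matching count. Under the plan's prior, negative means at most 1 response for n = 11, 12 or 13 (1/11 18.8%, 1/12 15.5%, 1/13 12.8%; 2/13 is 36.3%), and 0 responses for n = 6 to 10 (0/6 is 9.5%, 1/10 is 22.6%).
4. In 11.3, remove the word *eligible* so that all lead-in patients treated at the RP2D_c count towards DLT-E monitoring. Align the expansion-cohort sentence in 11.1 and the Synopsis; otherwise the change has no effect, because 11.3 counts only those lead-in patients who belong to that cohort.

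The cost is revised wording, one extra table, and an ORR that may be slightly lower if ineligible patients do not respond.

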11.2 STATISTICAL ANALYSES

11.2.1 GENERAL APPROACH

Frequencies and percentages will be used to summarize the distributions of categorical variables. Mean, median, range, inter-quartile range and standard deviation will be used to summarize distributions of continuous variables.

11.2.1.1 Participant Disposition

A detailed description of participant disposition will be provided at the end of the study, including a summary of the number and percentage of patients entered into the study, enrolled in the study, and treated, as well as the number and percentage of patients completing the study or discontinuing (overall and by reason for discontinuation).

11.2.1.2 Participant Characteristics

A summary of baseline patient and disease characteristics, historical diagnoses, pre-existing conditions, and prior therapies will be reported using descriptive statistics.

11.2.1.3 Concomitant Therapy

A summary of prior and concomitant medications by dose level (safety lead-in) and cohort (lead-in versus expansion) will be reported.

11.2.1.4 Treatment Compliance

Study treatment compliance will be assessed as the proportion of treatment actually taken relative to what is expected, after accounting for protocol-defined dose adjustments. For oral medications, study treatment taken will be derived from the difference between the total number of capsules/tablets dispensed and returned over the course of the patient's treatment. The number of cycles received, dose omissions, dose reductions, dose delays, and dose intensity will be summarized for all treated patients by dose level (safety lead-in) and cohort (lead-in versus expansion).

11.2.2 ANALYSIS OF THE PRIMARY EFFICACY ENDPOINT(S)

Objective response rate (ORR), defined as the proportion of patients who achieve a best overall response of CR or PR, is the primary efficacy endpoint. Tumor response will be measured and recorded using RECIST 1.1 guidelines (Eisenhauer et al. 2009). All lesions should be radiologically evaluated using the same method used for baseline evaluation. Any CR or PR will require confirmation at least 4 weeks following initial response observation. Objective response rate will be summarized for the ITT population using frequencies and proportions. A 95% CI for the ORR will be constructed using exact binomial (Clopper-Pearson) methods.

11.2.3 ANALYSIS OF THE SECONDARY EFFICACY ENDPOINT(S)

Disease control rate (DCR) is defined as the proportion of patients who achieve a CR or PR or SD for at least 2 cycles. DCR will be summarized for the ITT population using frequencies and proportions. A 95% CI for the DCR will be constructed using exact binomial (Clopper-Pearson) methods.

Best overall response (BOR) will be determined from a sequence of responses assessed. Two objective status determinations of CR before progression are required for a BOR of CR. Two determinations of PR or better before progression, but not qualifying for a CR, are required for a BOR of PR. A minimum timeframe of 8 weeks is required for a BOR of SD. BOR will be summarized for the ITT population using frequencies and proportions. A 95% CI for BORs of CR, PR, SD or PD will be constructed using exact binomial (Clopper-Pearson) methods.

Duration of response (DOR) will be evaluated only for responders. Duration of response is measured from the date of first confirmed response (CR or PR) to date of first disease progression (taking as reference for progressive disease the smallest measurements recorded since the treatment started) or death. DOR will be summarized graphically using Kaplan-Meier curves. Median DOR and corresponding 95% CI will be reported. For patients who are not known to have died or to have had a progression of disease as of the data-inclusion cut-off date, DOR will be censored at the date of last objective response assessment prior to the date of any subsequent systemic anticancer therapy.

Progression free survival (PFS) is defined as the time from the date of start of treatment to the first date of radiologically documented progressive disease or the date of death due to any cause, whichever occurs first. PFS will be summarized graphically using Kaplan-Meier curves. Median

PFS and corresponding 95% CI will be reported. For patients who are not known to have died or progressed as of the data-inclusion cut-off date, PFS time will be censored at the date of the last objective progression-free disease assessment prior to the date of any subsequent systemic anticancer therapy.

Overall survival (OS) is defined as the time from the date of start of treatment to the date of death due to any cause. OS will be summarized graphically using Kaplan-Meier curves. Median OS and corresponding 95% CI will be reported. For patients who are alive, lost to follow-up, or withdrawn from the study at the time of analysis, OS will be censored at the last date the patient is known to be alive.

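### The PFS and DOR censoring rule for new anticancer therapy depends on the patient's later outcome: event-free time after new therapy is dropped while later events are kept

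*Combined protocol and SAP*

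**What the plan says.** Section 11.2.3 defines the PFS event as "the first date of radiologically documented progressive disease or the date of death due to any cause, whichever occurs first". It makes no exception for events after new therapy, and neither do the endpoint definitions in sections 2.2 and 10.2.

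The censoring sentence applies to a restricted group: "For patients who are not known to have died or progressed as of the data-inclusion cut-off date, PFS time will be censored". For that group the date is fixed as "censored at the date of the last objective progression-free disease assessment prior to the date of any subsequent systemic anticancer therapy".

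DOR is built the same way. The sentence covers "For patients who are not known to have died or to have had a progression of disease as of the data-inclusion cut-off date, DOR", and the date is "censored at the date of last objective response assessment prior to the date of any subsequent systemic anticancer therapy".

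On the estimator, section 11.2.3 says "PFS will be summarized graphically using Kaplan-Meier curves", with a median and 95% CI; DOR is treated likewise. No section gives another rule, a sensitivity analysis or an estimand for new therapy. On size, section 11.1 says "an expansion cohort of up to 12 patients will be enrolled", a number that includes eligible lead-in patients treated at the selected dose.

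**The concern.** Kaplan-Meier estimation needs the decision to remove a patient from the risk set to be independent of what happens to that patient afterwards. Here it is not. Of two patients who start new therapy at the same time, the one who later dies stays at risk until death and counts as an event; the one who remains event-free is taken out before the therapy began.

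Two coherent rules exist: ignore new therapy for everyone, or censor everyone at it. The text applies the first to patients with a later event and the second to patients without one, so the curve and median estimate neither quantity.

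The situation can arise in this trial. Under section 9.3, clinical progression, unacceptable toxicity, withdrawal and use of a prohibited medication all end study treatment, but only radiological progression or death is a PFS event. Sections 9.2 and 9.4 list only survival status in long-term follow-up, at the investigator's discretion. Deaths after new therapy can therefore enter as events while scan-based event-free time may not be collected.

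**Working it through.** The plan gives no PFS or DOR assumption, so there is no stated figure to reproduce. The check has four steps.

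**1. Four invented patients, cut-off at 12 months.** A progresses at 4 months. B starts new therapy at 3 months (last scan at 2) and dies at 10. C starts new therapy at 3 months (last scan at 2) and is event-free at 12. D never switches and is event-free at 12.

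| Rule | Factor at 4 months | Factor at 10 months | 12-month PFS |
|---|---|---|---|
| Ignore new therapy | 3/4 | 2/3 | 50% |
| As written (C leaves at 2) | 2/3 | 1/2 | 33% |
| Censor everyone (B and C leave at 2) | 1/2 | no event | 50% |

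**2. General form.** Let T be the event time, U the start of new therapy and C the cut-off. As written, the patients at risk at time t are those with T ≥ t and C ≥ t, minus those with U < t and T ≥ C. Compared with ignoring new therapy, the events are identical and the risk set is never larger. Every factor 1 − d/n is then equal or smaller, so the curve can only be equal or lower.

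If U is independent of T and new therapy has no effect, the hazard is inflated by

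1 / (1 − F_U(t) · q(t)), where q(t) = P(T ≥ C | T ≥ t, C ≥ t).

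Assumptions, none from the documents: exponential times, median PFS 4 months, cut-off uniform over 6 to 18 months. At t = 6, with λ = ln 2 / 4 = 0.1733:

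- q(6) = (1 − e^(−12λ)) / (12λ) = 0.875 / 2.079 = 0.421.
- Median time to new therapy 8 months: F_U(6) = 1 − 2^(−6/8) = 0.405, so inflation is 1 / (1 − 0.171) = 1.21.
- Median time to new therapy 36 months: F_U(6) = 1 − 2^(−6/36) = 0.109, so inflation is 1 / (1 − 0.046) = 1.05.

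The shares who would ever switch before an event are (1/8)/(1/8 + 1/4) = 33% and (1/36)/(1/36 + 1/4) = 10%. Counting only switches before cut-off, they are about 31% and 9%.

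**3. Simulation under the same assumptions** (400,000 patients per scenario, censoring at the start of new therapy rather than at the preceding scan). The 6.8-month median is the sotorasib monotherapy figure in section 3.1.3, used only for scale; its shares are before any event, disregarding cut-off.

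| Median PFS | Share switching | 12-month PFS, true | As written | Median as written |
|---|---|---|---|---|
| 4.0 | about 9% | 12.5% | 11.2% | 3.97 |
| 4.0 | about 31% | 12.5% | 7.6% | 3.85 |
| 6.8 | 10% | 29.4% | 27.9% | 6.69 |
| 6.8 | 20% | 29.4% | 26.2% | 6.55 |
| 6.8 | 30% | 29.4% | 23.9% | 6.38 |

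Both coherent rules recover the true values in these scenarios. In 12,000 simulated trials of 12 patients (median 6.8 months), the written curve was never above the one ignoring new therapy. It was below it at 6, 9 or 12 months in 28%, 52% and 69% of trials as switching rose from 10% to 20% to 30%.

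**4. Against censoring everyone, the direction is not fixed.**

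- If new therapy works (hazard ratio 0.6, median 4 months, 30% switching, follow-up 6 to 30 months), 6-month PFS is 36.2% as written and 35.4% with everyone censored.
- If sicker patients switch sooner (shared log-normal frailty, SD 1, added to the 8-month scenario), true 12-month PFS is 20.8%; the written rule gives 17.1% and censoring everyone 25.9%.
- With the same frailty and about 8% switching, the figures are 20.9%, 20.0% and 22.3%.

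**The case against.** The strongest reply is that the obvious repair can do worse. Censoring everyone recovers the truth only when switching is unrelated to prognosis. Here one evident route to new therapy without a PFS event is clinical progression (section 9.3), and such patients are plausibly close to an event. In the frailty scenarios above, the written rule lies nearer the truth than censoring everyone. This stands: a reader might infer that censoring everyone is the unbiased answer, and the documents do not support that.

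A reader might also infer that the curves are biased downward whatever the target. That does not stand either. The sign is certain only against an analysis that ignores new therapy.

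Switching before an event may also be uncommon. Section 6.5.1 allows treatment beyond progression and section 8.2 prohibits other anticancer treatment on study, so much switching may follow an event already counted. The rate is unknown, which is why a range is given.

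Finally, the authors may have meant to censor everyone at new therapy and drafted loosely. That is possible, but the restriction to event-free patients appears in both sentences, and a programmer following them would implement the rule as analysed here.

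**Conclusion.** The point holds on the literal wording for both PFS and DOR. The rule uses the later outcome to decide who is censored, and its curve lies at or below the one that ignores new therapy. Relative to censoring everyone, the direction depends on whether new therapy works and why patients switch.

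Under the 4-month scenarios, 12-month PFS is too low by 1.3 points (12.5 − 11.2) at about 9% switching and by 4.9 points (12.5 − 7.6) at about 31%. These figures rest on exponential times, independent switching, new therapy without effect and the assumed follow-up.

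This is minor beside the noise. Even without censoring, the standard error of a 12.5% proportion in 12 patients is √(0.125 × 0.875 / 12) = 9.5 points. In simulated 12-patient trials at about 31% switching, the median shifted by 0.22 months on average, against a sampling SD of about 1.6 months; at 9% the shift was 0.07. DOR may rest on very few responders.

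A reader might infer that the trial's conclusion is at risk. It is not: the rule for calling the combination promising in section 11.1 uses ORR alone, and PFS and DOR have no test or threshold.

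**What to change.** In section 11.2.3, replace the restricted censoring sentence for PFS and for DOR with one rule that does not look at the later outcome. Either rule will do:

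- **Censor everyone:** any patient who starts new systemic anticancer therapy before progression or death is censored at the last assessment before it, whatever follows. This works with the current schedule. A few events after new therapy are no longer counted, and the curve can be biased upward if patients switch because of clinical progression.
- **Ignore new therapy:** count all events and all follow-up for everyone. This needs tumour assessments to continue after new therapy starts. Without them, event-free patients are last assessed before the therapy while deaths are still recorded, and the same asymmetry returns.

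Report the other rule as a sensitivity analysis where the data allow, and tabulate how many patients started new therapy before an event and why. The text change is about one sentence per endpoint. Censoring everyone needs no new patients or procedures; ignoring new therapy adds scans.
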